## 4. SELECTION, WITHDRAWAL, AND REPLACEMENT OF PATIENTS

### 4.1. Number of Patients Planned

Approximately 240 patients are planned to be enrolled into 3 groups (80 per group): dupilumab Q2W treatment groups (200 mg Q2W or 300 mg Q2W), dupilumab Q4W treatment group (300 mg Q4W), or placebo group. The study will be conducted at multiple sites in North America; other regions may be included.

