**6.2.5. Biomarker Procedures**

Thymus and activation-regulated chemokine and total serum IgE are markers of Th2 activity as downstream mediators in the IL-4/IL-13 signaling pathway ([Wirnsberger 2006](#), [Takeda 1997](#)). These analytes will be assessed as measures of Th2 activity and PD effect of dupilumab. The results may be used for modeling dupilumab activity with drug levels in the comparison of dosing regimens. Thymus and activation-regulated chemokine levels have also been closely associated with AD disease activity and severity ([Beck 2014](#)), and will be evaluated as an exploratory marker of efficacy. These markers may also be assessed for their potential value in predicting treatment response.

Lactate dehydrogenase levels have also been shown to correlate with disease severity and activity in patients with AD ([Mukai 1990](#)).

Patients with total serum IgE levels in the normal range may still have antigen-specific IgE in circulation, indicating they are atopic. To further understand atopy in this patient population, region-specific, allergen-specific IgE panels will be performed. These markers may be used to understand PD activity, efficacy, and may be also tested for predictive utility.

Serum samples for measurements of biomarkers (including TARC, total IgE, immunoglobulin profiling, allergen-specific IgE, and LDH [which will be measured as part of the blood chemistry]) to study the PD activity of dupilumab in pediatric AD patients will be collected at time points according to section 6.1.

Additional biomarker serum samples will be collected to study exploratory biomarkers of dupilumab activity and AD.

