### 5.12. Analysis of Biomarker Data

Descriptive statistics for the observed values, change from baseline and percent change from baseline values by treatment and visit will be provided for the following biomarker variables:

- TARC
- total serum IgE
- Serum Immunoglobulin profile (IgG/IgM/IgA, IgG subclasses)
- antigen-specific IgE
- Lactate dehydrogenase (LDH)

The Wilcoxon signed-rank test stratified by the baseline disease severity will be used to test if the change or percentage change from baseline value is significantly different from zero. P-value will be reported.

Exploratory analyses for the difference between dupilumab groups and placebo on the change from baseline and percent change from baseline values will be performed using a rank-based ANCOVA model with treatment group and the baseline disease severity as fixed effects, and the relevant baseline values as covariate. Missing value will be imputed by LOCF method for visits between post-baseline to week 16. After week 16, no imputation will be made. P-value for difference from placebo will be provided.

Correlation of baseline TARC (measured value) and IgE (measured value), absolute change or percent change from baseline value of baseline TARC (measured value) and IgE (measured value) with the following clinical endpoints will be explored using the Spearman's rho test. Both Spearman correlation coefficients and p-value will be reported.

- Percent change from baseline to week 16 in EASI score
- Percent change from baseline to week 16 in weekly average of peak daily pruritus NRS
- Change from baseline to week 16 in percent BSA
- Percent change from baseline to week 16 in SCORAD

Correlation of baseline TARC (measured value) and IgE (measured value) with the following clinical endpoints will be explored using the ANOVA model. The model includes the baseline biomarker data as the dependent variable, and treatment group, the responder/nonresponder of below clinical endpoint as the predictor variable. P-value will be provided to indicate significance of the responder/non-responder factor.

- IGA 0-1 at week 16
- EASI-75 at week 16
- improvement (reduction) of weekly average of peak daily pruritus NRS  $\geq 4$  from baseline to week 16

Association of positivity to at least one antigen-specific IgE with the following clinical endpoints will be explored using CMH test stratified by the baseline disease severity. The risk ratio and p-value from the chi squared test will be provided.

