- IGA 0-1 at week 16
- EASI-75 at week 16
- improvement (reduction) of weekly average of peak daily pruritus NRS  $\geq 4$  from baseline to week 16

Correlation/association will be implemented on the placebo, dupilumab Q2W, dupilumab Q4W and combined dupilumab (dupilumab Q2W and Q4W) groups, respectively.

All above analyses will be performed on the FAS for:

- All observed data, regardless if rescue treatment is used or data is collected after study drug withdrawal
- All observed data with censoring after rescue treatment use

The proportion of patients for whom biomarker concentrations “normalize” (shift from above normal to within the normal range) at Week 16 will also be evaluated.

The additional analysis will be performed on the following biomarkers at week 16:

- Serum total IgE
- Serum LDH

Serum total IgE and LDH are established clinical assays; the upper limit of normal (ULN) from the central lab reference range will determine the threshold for normal vs. elevated status.

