## 10. APPENDIX

### 10.1. Summary of Statistical Analyses

#### Efficacy Analysis:

Parameter(s)	Endpoints	Primary Statistical Method	Supportive/Sensitivity Statistical Method	Subgroup Analysis
Investigator's Global Assessment (IGA)	
 
IGA 0 to 1
 
reduction of <math>\geq 2</math> points from baseline
 
	
 
CMH test adjusted by randomization strata
 
	Yes for IGA 0 to 1, Cochran-Mantel-Haenszel test on OC or LOCF, and on PPS	Yes for IGA 0 to 1,
Eczema Area and Severity Index (EASI)	
 
EASI 75
 
EASI 50
 
EASI 90
 
% change from baseline
 
Change from baseline
 
	
 
CMH test adjusted by randomization strata for categorical variables
 
Multiple imputation (MI) with ANCOVA for continuous variables
 
	Yes for EASI-75 and % change, MMRM, ANCOVA for continuous variable, CMH on OC or LOCF for categorical variable	Yes for EASI-75 and % change
Pruritus Numeric Rating Scale (NRS)	
 
% change from baseline
 
reduction of <math>\geq 4</math> points from baseline
 
Change from baseline
 
	
 
CMH test adjusted by randomization strata for categorical variables
 
Multiple imputation (MI) with ANCOVA for continuous variables
 
	Yes for % change and reduction $\geq 4$	Yes for % change and reduction $\geq 4$
Pruritus Categorical Scale (PCS)	
 
Number (%) of patients
 
	
 
CMH test adjusted by randomization strata
 
	No	No
Body Surface Area (BSA) Involvement of Atopic Dermatitis	
 
% change from baseline
 
Change from baseline
 
	
 
Multiple imputation (MI) with ANCOVA
 
	No	No
SCORing Atopic Dermatitis (SCORAD)	
 
% change from baseline
 
Change from baseline
 
SCORAD50
 
SCORAD75
 
SCORAD90
 
	
 
Multiple imputation (MI) with ANCOVA for continuous variables
 
CMH test adjusted by randomization strata for categorical variables
 
	No	No

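### SAP 5.12: the unadjusted Spearman correlation of baseline TARC (and possibly IgE) with absolute BSA change is confounded by baseline BSA, so a marker of extent alone can look predictive in the dupilumab groups

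*SAP*

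**What the plan says.** SAP 5.12 describes the analysis as "Correlation of baseline TARC (measured value) and IgE (measured value), absolute change or percent change from baseline value of baseline TARC" and the corresponding IgE values, tested by Spearman's rho against four clinical endpoints. EASI, pruritus NRS and SCORAD enter as percent changes. BSA enters as "Change from baseline to week 16 in percent BSA", which is an absolute change in percentage points. On output the SAP says "Both Spearman correlation coefficients and p-value will be reported", and on groups "Correlation/association will be implemented on the placebo, dupilumab Q2W, dupilumab Q4W and combined dupilumab (dupilumab Q2W and Q4W) groups, respectively". No covariate, stratification or partial correlation is stated for these correlations.

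Protocol 6.2.5 gives the background: "Thymus and activation-regulated chemokine levels have also been closely associated with AD disease activity and severity". It adds: "These markers may also be assessed for their potential value in predicting treatment response". It makes no comparable statement about severity for total IgE, which it describes as a marker of Th2 activity.

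Other analyses do adjust. SAP 5.7.2 analyses continuous secondary endpoints, absolute BSA change among them, by ANCOVA with the baseline value in the model. Within SAP 5.12, the rank-based ANCOVA carries baseline severity and the baseline marker value, and the Wilcoxon and CMH analyses are stratified by baseline severity.

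**The concern.** Absolute BSA change depends on its own baseline. Entry requires at least 10% BSA, and the SAP 5.7 subgroups run from 10% to 50% and above, so a wide spread is expected. A 50% reduction is 5 points for a patient starting at 10% and 25 points for one starting at 50%. A marker that is higher in patients with more extensive disease will then go with larger point losses, even if it is unrelated to the proportion of disease cleared.

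A reader of the biomarker table could take a negative coefficient with a small p-value as evidence that baseline TARC predicts response. Because the dependence on baseline grows with the size of the improvement, the signal would be clearest in the dupilumab groups and weak in placebo. It could therefore pass for a treatment-specific predictor.

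**Working it through.** The plan states no operating characteristic for this analysis, so there is no figure to reproduce.

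**Inputs from the documents.** Group size is 80 ("Approximately 240 patients are planned to be enrolled into 3 groups (80 per group"), hence 160 for combined dupilumab. The BSA floor is 10%. There is no baseline adjustment.

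**Assumed, because the documents are silent.**
- Threshold: two-sided 0.05.
- Baseline BSA: truncated normal on 10 to 100, mean 55, SD 24.
- Marker: tied to baseline BSA only, at Spearman correlation r.
- Proportional BSA change: independent of both marker and baseline. Mean reduction 60% (SD 30%) or 50% (SD 40%) on dupilumab; 0 to 20% (SD 40 to 45%) on placebo.

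**Step 1: baseline BSA against absolute change.** Simulated at n=80 with a marker almost identical to baseline BSA, rho is -0.585 (60%/30%) and -0.411 (50%/40%). Under the placebo assumptions it is only -0.05 to -0.18.

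**Step 2: carry-over to an extent-only marker.** Approximately, rho(marker, change) = r × rho(baseline, change). For r=0.5 and 50%/40% this is 0.5 × (-0.411) = -0.206; simulation gives -0.209.

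**Step 3: chance of p<0.05.** By Fisher's z, the rate is about P(Z > 1.96 - atanh|rho| × sqrt(n-3)). The four corners, with the simulated rate beside each:
- n=80, 50%/40%, r=0.3: |rho|=0.123; 0.124 × sqrt(77) = 1.09; 19% (simulated 21%).
- n=80, 60%/30%, r=0.5: |rho|=0.293; 0.301 × sqrt(77) = 2.64; 75% (simulated 75%).
- n=160, 50%/40%, r=0.3: 0.124 × sqrt(157) = 1.55; 34% (simulated 35%).
- n=160, 60%/30%, r=0.5: 0.301 × sqrt(157) = 3.78; 97% (simulated 98%).

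Simulated rates in full:

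| r | n=80, 60%/30% | n=80, 50%/40% | n=160, 60%/30% | n=160, 50%/40% |
|---|---|---|---|---|
| 0.2 | 19% | 12% | 33% | 20% |
| 0.3 | 36% | 21% | 66% | 35% |
| 0.4 | 56% | 33% | 87% | 56% |
| 0.5 | 75% | 46% | 98% | 76% |

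Placebo (n=80) gives 5 to 19% for r from 0.1 to 0.7.

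**Step 4: sensitivity, r = 0.3, 0.4, 0.5.**
- Narrower baseline (mean 50, SD 15; 60%/30%): 27, 45, 62% at n=80.
- Stronger response (65%, SD 25%): 46, 73, 90% at n=80.
- 56 of 80 patients left after rescue censoring (60%/30%): 26, 41, 61%.
- Mean 55%, SD 35%, with latent-normal correlations of 0.3, 0.4, 0.5: 24, 40, 58% at n=80 and 44, 70, 89% at n=160; placebo-like response at n=80 gives 7, 8, 14%.

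**Step 5: the two candidate remedies.** With M the marker, C the change and B baseline BSA, the partial correlation is [rho(M,C) - rho(M,B) × rho(C,B)] / sqrt{[1 - rho(M,B)²] × [1 - rho(C,B)²]}. For r=0.5 and 50%/40%: (-0.209 + 0.5 × 0.411) / sqrt(0.75 × 0.831) = -0.004, so the artefact cancels. It rejects in about 4 to 7% of replicates under every response model tried.

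Percent change in BSA also rejects in about 4 to 7% when response is proportional, but that follows from the model. Suppose instead that the point reduction is independent of baseline (mean 25, SD 15, limited to baseline BSA). Percent change then rejects for the same uninformative marker in 25 to 60% at n=80 and 48 to 87% at n=160 (latent correlations 0.3 to 0.5). Absolute change rejects in only 6 to 8% and 8 to 16%.

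**The case against.** The strongest counter-argument concerns the null hypothesis. If the marker tracks extent and extent drives absolute change, the two really are associated, so rejecting independence is correct. The rates above are not type I error rates of the test as planned. That stands: they measure how often an extent-only marker would look predictive. Nor does the Protocol make prediction the main purpose. TARC and IgE are assessed mainly as pharmacodynamic measures, and prediction is something that may also be examined. It is still a stated use, and the unadjusted coefficient cannot serve it.

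The absolute metric also has a good reason, since it is the prespecified secondary endpoint. This stands, and it argues against replacing the metric. It does not justify omitting the baseline term that the ANCOVA of the same endpoint includes.

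The consequence is small. This is one of four endpoints in an exploratory analysis without multiplicity control, shown beside percent EASI and percent SCORAD, both of which incorporate extent. A signal confined to BSA would be noticeable. The sizes 80 and 160 are upper bounds, because SAP 5.12 uses observed data, once with censoring after rescue.

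A reader might infer that an extent marker will usually appear predictive, or that TARC and IgE are equally exposed. The documents support neither. They give no marker-BSA correlation, and they state a severity link for TARC only. At r=0.2 the single-group rate is 12 to 19%, and in placebo the dependence on baseline BSA is slight.

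**Conclusion.** The point holds as a limited one. The Spearman correlation with absolute BSA change mixes extent with response. If response is roughly proportional, a marker of extent alone can appear predictive in the dupilumab groups. Under the two main response scenarios, the false-signal rate is roughly 20 to 75% at n=80 and 35 to 98% at n=160 for marker-BSA correlations of 0.3 to 0.5. It is lower for weaker correlations, and about 5 to 20% in placebo.

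The correlations, the BSA distribution, the response sizes and proportionality itself are all assumptions. The case is reasonably firm for TARC and conditional for IgE. If response were additive rather than proportional, the absolute-change test would be little affected. No primary, secondary or hierarchical test is touched, so this is a desirable improvement and not a necessary correction.

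**What to change.** In the Spearman paragraph of SAP 5.12, keep absolute change in percent BSA and add that the partial Spearman correlation adjusted for baseline BSA will be reported in place of, or beside, the unadjusted coefficient, in each of the four groups.

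Do not simply substitute percent change in BSA. SAP 10.1 does list it in the row "Body Surface Area (BSA) Involvement of Atopic Dermatitis", so it is easy to produce. But it departs from the prespecified endpoint and moves the artefact if response is not proportional.

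The cost is one line of SAP text and one extra term in the correlation program. Baseline BSA is already collected, and no other analysis changes.

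### SAP 5.12 relates baseline TARC and IgE to response arm by arm, and no planned analysis estimates whether that association differs between dupilumab and placebo

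*SAP*

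**What the plan says.** Protocol section 6.2.5 names several uses for TARC and total IgE: Th2 activity, pharmacodynamic effect and, for TARC, an exploratory marker of efficacy. It then adds: "These markers may also be assessed for their potential value in predicting treatment response". Of the allergen-specific IgE panels it says that they "may be also tested for predictive utility".

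SAP section 5.12 turns this into the following analysis for IGA 0-1, EASI-75 and the 4-point NRS response:

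- The method is named first: "Correlation of baseline TARC (measured value) and IgE (measured value) with the following clinical endpoints will be explored using the ANOVA model".
- The marker is the outcome of that fit, not an explanatory term: "The model includes the baseline biomarker data as the dependent variable". Treatment and response status enter as main effects, with no product term.
- The only result reported is the p-value of the response-status effect.
- Each group is fitted on its own: "Correlation/association will be implemented on the placebo, dupilumab Q2W, dupilumab Q4W and combined dupilumab (dupilumab Q2W and Q4W) groups, respectively".

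The same section also plans Spearman correlations of baseline TARC and IgE with four continuous week 16 outcomes, and a CMH test of antigen-specific IgE positivity against response. Both are run by group in the same way. Treatment-by-subgroup interaction tests are planned in SAP section 5.7.3, but only for the subgroups listed in section 5.7, which include neither TARC nor IgE. Protocol section 9.5.6 makes the biomarker analyses exploratory and without multiplicity adjustment.

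**The concern.** A marker that predicts benefit from dupilumab is one whose link to response differs between dupilumab and placebo. A marker linked to response to the same degree in every arm is only prognostic. Telling the two apart needs an estimate of the difference between arms, and section 5.12 contains none. Its ANOVA has main effects only and is fitted within groups.

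That leaves the reader with a set of p-values to compare by eye. The groups carry very different amounts of information about the association, so an identical association can easily reach significance in one and not in the other. What is at stake is how an exploratory biomarker table is read, and possibly which marker is taken forward.

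There is a second, separate weakness. The ANOVA is specified on measured values and names no transformation, while the same section uses rank-based ANCOVA and Spearman for its other biomarker analyses. If TARC and IgE are right-skewed and are analysed untransformed, the ANOVA loses power.

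**Working it through.** **Inputs.** Section 5.12 states no numerical figure. The response rates and 80 patients per arm come from the sample size sections (protocol 9.2, SAP 2.2). With Fisher's exact test at two-sided 5%, those rates give power of 98.9, 88.1, 99.8, 99.4, 97.7 and 95.9% for IGA, EASI-75 and NRS (Q2W then Q4W each time). The plan states 98, 88, 99, 99, 97 and 95%, so its rates and powers agree and can be used here.

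**Responders per group** (rate × 80):

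| Endpoint | Placebo | Combined dupilumab (160) |
|---|---|---|
| IGA 0-1 | 0.09 × 80 = 7.2 | 0.37 × 80 + 0.29 × 80 = 29.6 + 23.2 = 52.8 |
| EASI-75 | 0.13 × 80 = 10.4 | 0.48 × 80 + 0.45 × 80 = 38.4 + 36.0 = 74.4 |
| NRS ≥4 | 0.11 × 80 = 8.8 | 0.38 × 80 + 0.36 × 80 = 30.4 + 28.8 = 59.2 |

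**Why by-arm p-values diverge.** In SD units of the marker, the standard error of the responder minus non-responder mean is √(1/n_R + 1/n_NR). For IGA:

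- placebo: √(1/7.2 + 1/72.8) = 0.391, so a difference of about 1.96 × 0.391 = 0.77 SD is needed for significance;
- combined dupilumab: √(1/52.8 + 1/107.2) = 0.168, so about 1.96 × 0.168 = 0.33 SD is needed.

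An equal observed difference anywhere between 0.33 and 0.77 SD is significant on dupilumab only. For a normal marker the expected difference is roughly the log odds ratio per SD: ln 1.5 = 0.41 and ln 2.0 = 0.69 both fall in that band.

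**Simulation of a purely prognostic marker.** The odds ratio per SD is the same in every arm, with the plan's rates and 80 per arm. The SAP's ANOVA is run in placebo and in combined dupilumab, and a treatment-by-marker test is run in one logistic model over all arms. Odds ratios and skewness are assumptions, because the documents give neither. Ranges cover the three endpoints and both a normal and an untransformed log-normal marker (log-SD 1), with 2000 trials per setting:

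| OR per SD | Significant, combined dupilumab | Significant, placebo | Dupilumab but not placebo |
|---|---|---|---|
| 1.0 | 4.5-5.8% | 5-6% | 4-5% |
| 1.25 | 19-28% | 8-12% | 17-25% |
| 1.5 | 50-69% | 17-24% | 37-54% |
| 2.0 | 90-98% | 39-50% | 47-60% |

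The interaction test rejected in 4.6-7.1% of trials throughout.

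With a more skewed marker (log-SD 1.2), IGA rates and odds ratios below 1, the last column is about 5, 12, 25 and 46% at OR 1.0, 0.8, 0.7 and 0.6, with the interaction test at about 5-6%. Taken together this is about 5% with no effect, 12-25% with a weak one and 25-60% with a moderate to strong one. Single settings at OR 0.6 with a normal or mildly skewed marker reach 62-64%.

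**Scale.** At OR 0.6 and log-SD 1.2, power in combined dupilumab is about 46% on the raw scale and 83% on the log scale; a second set of runs gave 55% and 85%. Over log-SD 0.8 to 1.5 the raw scale gave 68% down to 35%, against 83-85% on the log scale.

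**Power of the interaction.** For a marker with no effect on placebo and OR 0.7 to 0.5 per SD on dupilumab, the interaction test has about 16-35% power for IGA. A separate run at OR 0.6 gave about 22% for IGA and 26% for EASI-75.

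**The case against.** The strongest reply is that nothing here claims more than it delivers. The protocol says only that the markers may be assessed for prediction, after naming other uses. The SAP speaks of exploring correlation. Neither document calls any marker predictive of dupilumab response or sets a rule for doing so. This stands: the percentages above describe a reader who adopts the dupilumab-only rule, and are not the error rate of a planned test.

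It also stands that:

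- placebo is analysed too, and the Spearman correlations with continuous outcomes give a better-informed placebo comparison than 7 responders can. They still provide no estimate of the difference between arms.
- the treatment term, constant within a single arm, simply drops out there and is estimable in combined dupilumab. It is an untidy specification and does no harm to the result. If all arms were fitted together, an interaction term would still be missing.
- the label measured value mainly separates baseline level from change, so an untransformed analysis is a fair inference but is not stated outright.
- the interaction test would usually miss a real predictive marker of the size simulated. This argues for reporting an estimate with its interval, and is not a reason to leave the comparison out.

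**Conclusion.** The gap is real and modest. No planned analysis can separate prediction of benefit from prognosis for baseline TARC and IgE, and comparing by-arm p-values is a poor substitute because responder numbers are so unequal.

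Three stronger readings are tempting and not supported. First, that a prognostic marker will usually look predictive: this depends on a prognostic strength the documents do not give, and for a weak marker the pattern appears in only about 12-25% of trials. Second, that the untransformed scale causes the pattern: greater skew made it less frequent (64% falling to 34% as log-SD rises from 0.8 to 1.5 at OR 0.6), so scale is a power issue only, and only if the markers are skewed and left untransformed. Third, that the trial's conclusions are affected: the biomarker analyses are exploratory and outside the testing hierarchy, so no confirmatory result changes.

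**What to change.** In SAP section 5.12 add, for each marker and each of the three binary endpoints, one logistic model over all randomized arms: response on log(baseline marker), treatment, marker-by-treatment interaction and the randomization strata. Report the interaction estimate with its 95% confidence interval and the marker odds ratio in each arm. State whether the interaction contrasts each regimen or combined dupilumab with placebo. Keep the by-arm results and label them as associations only.

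The cost is a paragraph of SAP text and 2 markers × 3 endpoints = 6 models (12 if repeated under both of the section's rescue-handling rules). No new data are needed, and section 5.7.3 already uses logistic regression with a treatment interaction for subgroups.

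The downside is the low interaction power shown above. The report should say that a non-significant interaction is not evidence that a marker lacks predictive value.
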